10.1.2.2. Hypothesis #2: Difference in Quantitative Flortaucipir Uptake Between Fighter Groups

The mean flortaucipir SUVr difference between fighting groups (active vs retired) will be tested with the following hypothesis.

$$H_0 : \mu_{Act} = \mu_{Ret}$$

$$H_A : \mu_{Act} \neq \mu_{Ret} ,$$

Where:

- μ_{Act} is the mean flortaucipir SUVr in the active fighters
- μ_{Ret} is the mean flortaucipir SUVr in retired fighters

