10.1.3. Primary Analysis

Descriptive statistics for flortaucipir SUVr will be reported overall and by each enrolment group. Box-and-whisker plots of flortaucipir SUVr will be created to visually display tau distribution across these groups.

Hypotheses 1 and 2 will be tested using a two-way ANOVA, with fighters status (active or retired) and cognitive status (impaired or normal) as two main factors. The comparisons of mean SUVr values will be compared through setting up proper contrasts.

The descriptive statistics and ANOVA analysis will be summarized in a table and include the following:

- n
- Mean (SD)
- Median
- Min, Max
- Overall P-value from ANOVA
- P-values from each contrast

Hypotheses 3 and 4 will be tested using Fisher's exact test. The distributions for each enrollment group will be presented in a 4x2 contingency table along with the p-values from each test.

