10.1.4. Exploratory Analysis

A correlation analysis will be performed to investigate the relationship between flortaucipir SUVR and:

- MMSE
- Beck Depression Inventory II
- Digit span forward/backward
- MRI brain volumes (normalized to intracranial volume)
 - Whole brain volume
 - Gray volume
 - Hippocampal volume
 - Ventricle volume

Contingent on a trending significance in the primary analysis ($p \leq 0.1500$ for contrasts), more correlation analysis will be performed to investigate the relationship between tau deposition as measured by flortaucipir SUVR and:

- Years of fighting
- Age when fighting began
- Number of bouts
- Number of losses
- Number of wins
- Number of draws
- Number of knockouts

A multivariate model may also be derived assuming strong relationships found in the primary and correlation analyses.

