10.1.4.1. Subgroup Analysis

All correlation analysis conducted will be performed for each cognitive group separately, and results will be provided in a table.

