1.1.2. HYPOTHESIS #1 AND #2

```
ods output contrasts=contrasts;
PROC GLM data = <data>;
class FIGHTGRP COGGRP;
model SUVR = FIGHTGRP COGGRP FIGHTGRP*COGGRP;
contrast "Active vs. Retired"      FIGHTGRP 1 -1;
contrast "CI vs. CN"              COGGRP 1 -1;
RUN;
QUIT;
```

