1.1.4. HYPOTHESIS #4

```
PROC FREQ data = <data>;
table VISREAD*FIGHTGRP / fisher;
RUN;
```

1.2.SAMPLE CODE FOR EXPLORATORY ENDPOINT

```
ods output PearsonCorr=corr;  
PROC CORR data = <data> pearsons;  
var <variable list>;  
RUN;
```

1.3.SAMPLE CODE FOR TEAE TABLES BY DESCENDING FREQUENCY

```
ods output crosstabfreqs=xtab;  
PROC FREQ data = <data> order=freq;  
table <SOC variable>*<Preferred Term variable>;  
RUN;
```

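### The SUVR correlations are split by cognitive group but neither split by nor adjusted for active/retired status, so a level difference between fighter groups cannot be told from a relation within them

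*SAP*

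**What the plan says.** SAP 10.1.4 commits to the following: "A correlation analysis will be performed to investigate the relationship between flortaucipir SUVR and" MMSE, Beck Depression Inventory II, digit span forward/backward, and four MRI volumes normalised to intracranial volume. SAP 10.1.4.1 gives the only stratification: "All correlation analysis conducted will be performed for each cognitive group separately". The sample code in Appendix II 1.2 is "PROC CORR data = <data> pearsons" with a VAR list and no PARTIAL or BY statement.

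The primary analysis is different. SAP 10.1.3 specifies a two-way ANOVA "with fighters status (active or retired) and cognitive status (impaired or normal) as two main factors", coded in Appendix II 1.1.2 as "model SUVR = FIGHTGRP COGGRP FIGHTGRP*COGGRP". Hypothesis 2 (SAP 10.1.2.2) asks directly whether SUVR differs by fighter status: "The mean flortaucipir SUVr difference between fighting groups (active vs retired) will be tested with the following hypothesis".

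Adjustment of the correlations is only a possibility: "A multivariate model may also be derived assuming strong relationships found in the primary and correlation analyses". No covariates are named for that model.

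The protocol synopsis plans about 15 active and 15 retired fighters, each with about 10 impaired and 5 unimpaired.

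**The concern.** Fighter status defines enrolment and enters the primary model, but drops out of the correlations. If active and retired fighters differ in mean SUVR and also in mean score or brain volume, the correlation within a cognitive group is pulled away from the relation that holds among active fighters and among retired fighters. It can be non-zero when neither fighter group shows a relation, or close to zero when both do.

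At stake is the reading of the second primary objective, the relationship between clinical presentation and tau uptake in active and retired fighters. A notable correlation might only restate that retired fighters differ from active ones, and a real relation might be passed over. The optional multivariate model would not catch the second case, because it is considered only after strong relationships have been seen.

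**Working it through.** **Plan's own figure.** There is none to reproduce. SAP 3.2 reports no formal sample size calculation, and neither document gives an SD, an effect size or an active/retired difference.

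**Inputs from the documents.** Impaired group: 10 + 10 = 20. Unimpaired group: 5 + 5 = 10. All sizes are approximate. The 0.05 level is in SAP 10.1.3.1, under the primary analysis; applying it, two-sided, to the correlations is an assumption.

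**Other assumptions.** Normal data, an equal active/retired split, and the same within-group correlation rho in both fighter groups. dx and dy are the active-retired differences in the two variables, in within-group SDs.

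**Formula.** The population correlation in the equal mixture is

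r = (rho + dx·dy/4) / sqrt[(1 + dx²/4)(1 + dy²/4)].

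- rho = 0, shifts 1 and 1: r = 0.25/1.25 = 0.20, with no relation in either fighter group.
- rho = 0.5, shifts 1 and -1: r = (0.5 - 0.25)/1.25 = 0.20, so the relation is largely hidden.
- rho = 0.5, shifts 1 and 1: r = (0.5 + 0.25)/1.25 = 0.60, so it is strengthened.

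**Simulation.** At least 100,000 runs per setting, comparing the Pearson t-test (n-2 df) with the partial correlation given fighter status (n-3 df).

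Rejection with no within-group relation (rho = 0):

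| Shift in both variables (SD) | Pearson, n=10 | Pearson, n=20 | Partial |
|---|---|---|---|
| 0.5 | 5% | 6% | 5% |
| 0.8 | 7% | 9% | 5% |
| 1.0 | 9% | 14% | 5% |
| 1.5 | 19% | 38% | 5% |

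If only one variable shifts (1 SD and 0), Pearson stays at 5%.

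Power with a within-group correlation of 0.5:

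| Shifts (SD) | Pearson, n=10 | Partial, n=10 | Pearson, n=20 | Partial, n=20 |
|---|---|---|---|---|
| None | 33% | 29% | 64% | 62% |
| 0.5, opposing | 21% | 29% | 44% | 62% |
| 0.8, opposing | 10% | 29% | 22% | 62% |
| 1.0, opposing | 5% | 29% | 10% | 62% |
| 1.0, same direction | 51% | 29% | 85% | 62% |

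Opposing means that the product of the two shifts has the opposite sign to the within-group correlation. The loss of power starts at smaller shifts than the false rejection does.

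**Scale.** For comparison, with cells of 10, 5, 10 and 5 the Hypothesis 2 contrast has standard error 0.5 × sqrt(1/10 + 1/5 + 1/10 + 1/5) = 0.387 SD on 30 - 4 = 26 df. It needs about (2.06 + 0.86) × 0.387 = 1.13 SD for 80% power. The SUVR shift that Hypothesis 2 is well placed to detect is therefore in the range where the correlations are affected, provided the other measure shifts too. This does not show that such a shift exists.

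**The case against.** **The correlations are not the only evidence for objective 2.** A reader might infer that objective 2 rests on them. It does not. Hypothesis 1 compares SUVR by cognitive status in a model that already contains fighter status and its interaction, and Hypothesis 3 relates a four-level visual read to cognitive status. The correlations supplement these, and four of the listed measures are MRI volumes rather than clinical presentation. This stands.

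**The marginal correlation is a legitimate quantity.** The objective speaks of active and retired fighters together, and the documents do not say whether fighter status is a nuisance or a marker of cumulative exposure. If it is a marker, conditioning on it removes relevant signal. A reader might infer that Pearson is invalid and should be replaced by the partial value; the documents do not support that. This also stands, and it argues for showing both values.

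**The tests are exploratory.** SAP 10.1.2 says so for all of them, and no decision rule is attached to the correlations with baseline measures. Rejection rates here measure how far a result could mislead; they are not a breach of an error guarantee.

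**The sizes are assumed.** False rejection needs sizeable shifts in both variables, and the documents report none. An equal split is also assumed, while group sizes are approximate and enrolment stops administratively.

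**The code is only a template.** It also lacks the cognitive-group split that the text requires, so a missing PARTIAL statement proves little alone. But the text of 10.1.4 and 10.1.4.1 does not mention fighter status either, so the gap does not depend on the code.

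**Adjustment is incomplete.** Conditioning on fighter status leaves age unadjusted. True, but no reason to omit a factor the trial already enrols and models by.

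**Conclusion.** The point holds as a question of interpretation. As written, the correlations cannot distinguish a relation within fighter groups from a difference in level between them, and the optional multivariate model does not reliably fill the gap.

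The size depends on shifts the documents do not give. False rejection is negligible at 0.5 SD in both variables and becomes material from about 0.8 to 1 SD. Masking needs shifts that oppose the within-group relation; it is already visible at 0.5 SD and severe at 1 SD.

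The documents do not support reading this as an inflated confirmatory error rate, as a flaw in the primary ANOVA, or as evidence that active and retired fighters do differ in these measures. It is a worthwhile, low-cost improvement to exploratory reporting.

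**What to change.** In SAP 10.1.4 and Appendix II 1.2, report beside each planned Pearson correlation, within each cognitive group, the partial correlation given fighter status (PROC CORR with a PARTIAL statement on a 0/1 FIGHTGRP variable). State whether any association described for objective 2 persists within fighter groups. Keep the Pearson values, and do not rest the objective 2 statement on the partial value alone.

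Cost: one SAP sentence, one line of code, one extra column in the table, and no new data. The partial value uses one degree of freedom, about 1 to 4 points of power if the groups do not differ. It also leaves out any between-group association, so it has lower power than Pearson when the shifts agree in direction with the within-group relation: a gap of about 22 to 23 points for shifts of 1 SD, at n=10 and n=20. Showing both values lets the reader see which situation applies.

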5.3 Selection of Subjects

5.3.1 Inclusion Criteria

All subjects must meet all of the following criteria to enroll in this trial:

1. Males that have consented, are currently enrolled in the PFBHS protocol, and have participated in a minimum of 10 professional fights;
2. Can tolerate PET scan procedures; and
3. Have the ability to provide informed consent for study procedures (if the patient is ineligible to give informed consent, based on local standards, the patient's legal representative may consent on behalf of the patient, but the patient must still confirm assent).

Subjects with cognitive impairment should meet the following criteria:

1. Have subjective cognitive complaints or objective decline or impairment as determined by the investigator.

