1. INTRODUCTION

Chronic traumatic encephalopathy (CTE) is a neurodegenerative disease marked by widespread accumulation of hyperphosphorylated tau (p-tau), predominantly as neurofibrillary and astrocytic tangles. CTE has been found most often in professional athletes involved in contact sports (e.g. boxing, American football) who have been subjected to repetitive brain trauma, including mild traumatic brain injury (TBI) or even asymptomatic, subconcussive trauma.

The Professional Fighters Brain Health Study (PFBHS) being conducted at the Cleveland Clinic Lou Ruvo Center for Brain Health is a longitudinal study that focuses on a sample of active and retired professional fighters, and compares them with a control cohort matched for age and level of education. The primary objective of the PFBHS is to determine the relationship between measures of head trauma exposure and other potential modifiers and changes in brain imaging, neurological and behavioral function over time. In this context, the addition of an imaging biomarker that could identify the presence of underlying tau pathology might be useful in understanding the etiology and evolution of chronic traumatic encephalopathy (CTE), and could potentially identify cases at risk for subsequent neurodegeneration or other clinically important outcomes with implications for management of CTE and/or TBI cases.

Flortaucipir (¹⁸F-AV-1451) may be useful as a marker of tau pathology in patients with Alzheimer's Disease (AD) and other neurodegenerative disorders. Several preliminary studies using flortaucipir have been completed (e.g., Chien et al., 2013). Based on this rationale, the goal of this protocol is to perform flortaucipir PET imaging on active and retired professional fighters enrolled in the PFBHS protocol and explore its potential as a biomarker for CTE.

The purpose of this statistical analysis plan (SAP) is to describe the statistical analyses for this protocol. The SAP should be read in conjunction with the protocol.

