2. STUDY OBJECTIVES

2.1. Primary Objective

The primary objectives of this study are:

- To explore the use of flortaucipir as a biomarker for brain injury related to repetitive head trauma; and
- To examine the relationship between clinical presentation and tau deposition as measure by flortaucipir uptake in active and retired professional fighters.

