10. EFFICACY ANALYSIS

10.1. Primary Efficacy Analysis

10.1.1. Efficacy Variable

The relationship of flortaucipir uptake will be evaluated both quantitatively (SUVr) and qualitatively using assessments from a visual read of the signals from images, classifying scans as ‘No uptake’, ‘Mild uptake’, ‘Moderate uptake’, and ‘Intense uptake’.

The flortaucipir PET SUVr will be generated as an average SUVr across selected AAL defined regions and a weighted average (MUBADA) SUVr based on regions used in other studies to discriminate among AD and control groups.

Efficacy analyses will be conducted separately on these two sets of SUVr and the qualitative read.

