10.1.2. Hypothesis Tests

There are no formal hypothesis testing planned for this study. All the statistical hypothesis testing described below are for exploratory purpose only.

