10.1.3.1. Statistical Considerations in Primary Analysis

All hypothesis testing will be run at the 0.05 level of significance. Because this is a Phase I study, no correction for multiplicity will be applied to control for alpha.

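### The only planned analyses using a measure of fight exposure run only if contrasts that do not measure exposure reach p ≤ 0.15, and the SAP does not say whether one or both must do so

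*SAP*

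**What the plan says.** The first primary objective (SAP 2.1) is "To explore the use of flortaucipir as a biomarker for brain injury related to repetitive head trauma". SAP section 1 sets the trial within a parent study whose own aim is to "determine the relationship between measures of head trauma exposure and other potential modifiers and changes in brain imaging".

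The primary SUVr analysis (SAP 10.1.3; code in Appendix II, 1.1.2) is a two-way ANOVA with interaction on career status and cognitive status. It has two contrasts: active against retired, and impaired against normal. On these the SAP says "The comparisons of mean SUVr values will be compared through setting up proper contrasts". Every subject must "have participated in a minimum of 10 professional fights" (Protocol 5.3.1), so there is no unexposed group and neither factor is defined by amount of exposure.

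SAP 10.1.4 then has two tiers of correlation with SUVr:

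- **Unconditional:** MMSE, Beck Depression Inventory II, digit span and four MRI volumes.
- **Conditional:** years of fighting, age at which fighting began, and numbers of bouts, losses, wins, draws and knockouts. These are done "Contingent on a trending significance in the primary analysis", with the threshold p ≤ 0.15 for contrasts.

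SAP 10.1.4.1 has all correlations done separately in each cognitive group. On inference, the SAP states "All the statistical hypothesis testing described below are for exploratory purpose only" (10.1.2) and "no correction for multiplicity will be applied to control for alpha" (10.1.3.1).

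**The concern.** The seven fight-history variables appear in no other planned analysis. The group comparisons, visual read, cognitive scores and MRI volumes all bear on the objective, but none uses an exposure measure. The possible multivariate model at the end of 10.1.4 is optional, depends on earlier findings and names no covariates.

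The condition tests a different question from the one it controls. Bouts or knockouts can track SUVr within every cell while both group contrasts are null. Followed as written, the plan would then omit its only prespecified look at whether tau signal rises with exposure, even when it does. A labelled post hoc analysis would remain possible, so what is lost is prespecified status.

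The rule is also incomplete. With two contrasts, it does not say whether one passing is enough. Two analysts could follow the SAP and produce different outputs, with the choice made after the p-values are known.

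This is not a claim that the reported correlations would be biased or that a confirmatory error rate is inflated.

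**Working it through.** The plan has no figure to reproduce: SAP 3.2 says no sample size calculation was made, and 0.15 is a rule rather than a result.

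**Inputs from the documents.** Planned cells are 10 impaired and 5 normal among active fighters, and the same among retired fighters (Protocol synopsis), so n = 30 and residual df = 30 − 4 = 26. The model is the one in SAP Appendix II, 1.1.2. The correlations are Pearson (Appendix II, 1.2) at 0.05 (10.1.3.1), taken as two-sided.

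**Assumptions.** Within-group exposure–SUVr correlation r = 0.5. SUVr and exposure each have within-cell SD 1. One SUVr set decides its own correlations, which is the natural reading of "Efficacy analyses will be conducted separately on these two sets of SUVr and the qualitative read" (10.1.1).

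**Step 1: what a contrast needs to pass.** Its variance is 0.25 × (1/10 + 1/5 + 1/10 + 1/5) = 0.15 SD², and the two contrasts are orthogonal. The critical t (26 df, 0.075 per tail) is 1.483, so the observed difference must be at least 1.483 × √0.15 = 0.57 SD.

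**Step 2: how often the condition is met.** With no group difference:

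- either contrast: 1 − 0.85² = 0.2775
- both contrasts: 0.15² = 0.0225

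That is about a 12-fold difference between the two readings. If retired and impaired fighters are each 1 SD more exposed, mean SUVr shifts by 0.5 × 1 = 0.5 SD on each factor. The noncentral t then gives 0.434 per contrast, so either is 1 − 0.566² = 0.68 and both is 0.434² = 0.19.

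**Step 3: chance that the correlation is run and reaches p < 0.05.** Simulation, 60,000 runs per scenario. The last three columns go from unconditional to conditional, with either contrast sufficing.

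| Scenario (r = 0.5) | Condition met: either / both | Impaired, n=20 | Normal, n=10 | Pooled, n=30 |
|---|---|---|---|---|
| Exposure unrelated to group | 27% / 3% | 64 → 17% | 33 → 9% | 83 → 23% |
| Retired and impaired each +0.5 SD exposure | 40% / 6% | 67 → 27% | 35 → 15% | 86 → 36% |
| Retired +1 SD exposure | 51% / 7% | 74 → 40% | 40 → 25% | 90 → 48% |
| Retired and impaired each +1 SD exposure | 67% / 20% | 73 → 51% | 40 → 30% | 94 → 65% |
| Retired +1 SD exposure; impaired +0.8 SD SUVr | 84% / 32% | 74 → 62% | 40 → 34% | 85 → 71% |
| Both +1 SD exposure; impaired +0.5 SD SUVr | 92% / 38% | 74 → 68% | 40 → 37% | 97 → 90% |
| SUVr +0.8 SD on both factors; exposure unrelated | 92% / 53% | 56 → 51% | 28 → 25% | 69 → 63% |

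The simulated rates for meeting the condition agree with Step 2 (0.274 / 0.026 with no group difference; 0.674 / 0.197 with 1 SD on both factors). If both contrasts must pass, the n = 20 figure falls to about 2% in the first row, 15% in the fourth and 28% in the last. In the first scenario at n = 20, r = 0.4 gives 43 → 11% and r = 0.6 gives 84 → 23%.

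**Step 4: what the condition saves.** If nothing is related to anything, each test is run and falls below 0.05 with probability about 0.014, against 0.05 unconditionally. By cognitive group there are 7 × 2 SUVr sets × 2 groups = 28 tests: 28 × 0.05 = 1.4 chance positives against 28 × 0.014 = 0.39. Adding pooled results makes 42 tests: 2.1 against 0.59.

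**The case against.** **It is a design choice in an exploratory tier.** Staging a second-tier look in about 30 subjects is legitimate, and the condition does reduce chance findings (Step 4). This stands as a cost of removing it. It does not justify a trigger that is not about exposure. In hypothesis-generating work, null or imprecise exposure estimates are also informative.

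**The large losses need exposure to be unrelated to group and SUVr not to differ by group.** That fits poorly with a rationale linking trauma, tau and clinical presentation. This stands in part. When SUVr itself differs clearly by group, the loss at n = 20 is about 5 to 12 points. When only exposure differs, by 1 SD on both factors, it is still 23 points.

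**The pooled test is not clearly planned.** Correct: 10.1.4.1 clearly plans only the by-group tests, so the n = 20 and n = 10 columns carry the point. At n = 10 there is little power to lose.

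**There are two SUVr sets, so at least one may qualify.** Also fair. With an assumed residual correlation of 0.8 between the sets, at least one meets the condition about 37% of the time rather than 27% in the unrelated case, and 77% rather than 67% with 1 SD on both factors. The omission is less likely, but not removed.

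**One contrast sufficing is the natural reading.** The SAP speaks of a trend in the singular and reports a p-value for each contrast. That is reasonable, and the main figures use it, but the text does not say so and the alternative gives very different results.

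**Conclusion.** The concern holds and should be fixed. Both parts rest on the text alone: the only exposure analyses depend on contrasts that do not measure exposure, and the rule does not say whether one or both contrasts must pass.

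The size depends on assumptions the documents do not supply. Across the scenarios at r = 0.5, with either contrast sufficing, the chance of running and detecting the correlation falls by about 5 to 47 percentage points in the impaired group and 3 to 24 in the normal group (6 to 60 if pooled). The upper ends apply when exposure is unrelated to group and SUVr does not differ by group; the lower ends apply when SUVr differs clearly by group.

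**What to change.** In SAP 10.1.4, replace the sentence that sets the condition with:

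> Correlations of flortaucipir SUVr (each of the two sets) with the following will be performed regardless of the primary-analysis p-values, in the whole efficacy population and by cognitive group. Estimates with 95% confidence intervals will be reported. These analyses are exploratory and unadjusted.

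State the number of tests in the report, with the number expected below 0.05 by chance. If the condition is kept, say whether one or both contrasts must reach p ≤ 0.15.

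The cost is one sentence and its tables. The variables are already listed, and Protocol 8.1 provides for transfer of parent-study data, including history, to the sponsor. It does not name fight records, so their inclusion should be confirmed. The price is about one extra chance positive in 28 tests (1.4 − 0.4 = 1.0), or 1.5 in 42 (2.1 − 0.6).

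Estimates will be imprecise. By Fisher's z, tanh(0.549 ± 1.96/√(n − 3)), an observed r of 0.5 has a 95% interval of −0.19 to 0.86 at n = 10, 0.07 to 0.77 at n = 20 and 0.17 to 0.73 at n = 30. The intervals should therefore be reported, not only the p-values.
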